## JHM IRB - eForm A – Protocol

- Use the section headings to write the JHM IRB eForm A, inserting the appropriate material in each. If a section is not applicable, leave heading in and insert N/A.
- When submitting JHM IRB eForm A (new or revised), enter the date submitted to the field at the top of JHM IRB eForm A.

\*\*\*\*\*

### 1. Abstract

- a. Provide no more than a one page research abstract briefly stating the problem, the research hypothesis, and the importance of the research.

Obstructive sleep apnea (OSA) is a common disorder affecting 24% of men and 9% of women in the United States. OSA causes repetitive upper airway closure during sleep, resulting in hypoxemia, hypercapnia, and arousals. OSA induces cardiometabolic dysfunction including insulin resistance, dyslipidemia, and endothelial dysfunction, culminating in increased rates of diabetes and cardiovascular mortality. We have accumulated evidence that OSA acutely increases levels of glucose and free fatty acids (FFA) during sleep, reflecting insulin resistance and excessive adipose tissue lipolysis. Repetitive nocturnal increases in glucose and FFA may eventually lead to diabetes and cardiovascular disease[1]. In animal studies, we have shown that intermittent hypoxia simulating OSA causes adipose tissue lipolysis, which is attenuated by beta blockade with propranolol [2]. **Thus, we hypothesize that acute metabolic changes in OSA are mediated by sympathetic activation, and are preventable by beta blockade.** This challenges the prevailing view that OSA causes metabolic dysfunction through hypoxia or re-oxygenation injury [3]. We will test this hypothesis in a randomized double blind placebo controlled, cross-over study of propranolol taken before sleep in patients with OSA.

### 2. Objectives (include all primary and secondary objectives)

Our primary objective is to test whether propranolol lowers glucose and FFA levels during sleep in OSA, and preserves vascular function (EndoPAT) versus placebo. Our secondary objective is to test whether propranolol influences sleep quality, architecture, and hemodynamics in OSA. Additional outcomes of interest are effects of OSA, CPAP, and propranolol on lipolysis and fatty acid oxidation, as measured with stable isotopes; and circulating genetic/epigenetic changes.

We also will collaborate with the National Institutes of Health (NIH) on an ancillary study of energy expenditure under each study condition, to be performed in a whole-body calorimeter, in the laboratory of [name] (NIDDK). The procedures are briefly described here, but the participants will have a separate written consent process. The extent of what is to be performed in the PROSAT study is consenting participants to being contacted by the NIH for potential enrollment in their study.

### 3. Background (briefly describe pre-clinical and clinical data, current experience with procedures, drug or device, and any other relevant information to justify the research)

20 million adults in the United States[4] and >100 million adults worldwide [5] have OSA, and the prevalence continues to rise with obesity[6]. These figures are especially alarming as OSA is associated with diabetes [7-9], cardiovascular disease (CVD) [10-13], and mortality [14, 15]. However, mechanisms linking OSA to these outcomes are unclear. As a result of this knowledge gap, fundamental questions such as what features of OSA are most harmful, and which patients can safely decline treatment, cannot be answered. Moreover, therapies for OSA such as CPAP are poorly tolerated, leaving non-adherent

patients susceptible to CVD. Equally problematic, OSA patients who might not be at increased risk for CVD may be burdened with CPAP or invasive (and often ineffective) surgical procedures [16, 17].

[figure not shown]
We have observed that OSA acutely and dynamically elevates levels of FFA and glucose during sleep (fig 1). These changes, if recurring nightly, may foster progression towards diabetes and CVD. In mice, we showed that inhibiting the sympathetic nervous system (SNS) by surgical and pharmacologic methods during exposures to simulated OSA prevented these metabolic changes. Thus, we hypothesize that catecholamines lead to excessive FFA and glucose mobilization during sleep which can in turn lead to insulin resistance, hyperlipidemia, and vascular dysfunction. In this project we will examine whether these metabolic changes can be prevented by beta blockade, and we will use stable isotopes to quantify FFA metabolism including rates of lipolysis (glycerol and palmitate infusions) and fatty acid oxidation (palmitate ingestion).

We are also interested in interactions between OSA and genetics. Recently, our group discovered epigenetic and transcriptional changes associated with sleep apnea. In a cohort of Andean highlanders from the CRONICAS cohort study in Puno, Peru (3825m above sea level) we showed that sleep apnea was associated with differential methylation of protein tyrosine phosphatase, receptor type N2 (PTPRN2), which plays a role in the secretion of insulin and neurotransmitters. We also identified differentially methylated regions in pathways that regulate energy utilization, including mitogen activated protein kinase (MAPK), a regulator of insulin signaling ( $p=10^{-4}$ ) and Peroxisome Proliferator-Activated Receptor (PPAR) ( $p<0.01$ ). These findings are not limited to high altitude conditions; intermittent hypoxia exposure in healthy volunteers up-regulated pro-inflammatory gene toll receptor 2 (TLR2) in peripheral blood mononuclear cells (Polotsky et al, PLoS One 2015). These findings collectively show that sleep apnea at high altitude, and intermittent hypoxemia at sea level are associated with genetic changes that predispose to diabetes and cardiovascular disease. It is not yet known whether OSA at sea level leads to a similar epigenetic and inflammatory signature. Therefore we will also examine epigenetic and transcriptional impacts of exposure to OSA, focusing on the methylated regions identified in the cross-sectional analysis above, and on the transcription of TLR2.

In a preliminary study described below, we illustrate our discovery that OSA (elicited by CPAP withdrawal in study NA\_00086830) leads to nocturnal metabolic dysfunction.

### Preliminary Studies:

**Methods:** OSA patients (AHI>20, age 20-65) acclimated to CPAP were studied while sleeping with CPAP, or on the third night after CPAP withdrawal. During sleep, from 10:40 PM to 6:40 AM, we measured serum FFA, glycerol, insulin, glucose, and triglycerides every 20 minutes via an indwelling IV. Upon awakening, we performed an oral glucose tolerance test (OGTT) and peripheral artery tonometry (EndoPAT) to assess reactive hyperemia index (RHI). We compared effects of OSA versus CPAP in the same subjects on two different nights, one to 4 weeks apart. **Results:** 18 patients (13 men, 5 women) completed most aspects of the study to date. CPAP withdrawal led to re-emergence of OSA (CPAP AHI:  $4.9\pm0.9$ , vs. OSA AHI:  $66.7\pm7.5$ ; mean  $\pm$  SEM,  $p<0.001$ ). Fig. 1

[figure not shown]

**Figure 1. OSA increases nocturnal FFA, glucose, and insulin.** Blood was sampled at 20 min intervals beginning at 10:40 PM (lights out) until 6:40 AM (lights on, dashed line). The same 18 patients were studied asleep wearing CPAP (red) or with OSA (on the third night after stopping CPAP, blue). Lines depict mean  $\pm$  SEM.

demonstrates that OSA also increased nocturnal FFA, glucose, insulin, and triglycerides (trend) compared to CPAP. Glycerol measured in 7 subjects was also elevated (CPAP:  $0.17 \pm 0.06$ ; OSA:  $0.29 \pm 0.11$  mmol,  $p=0.04$ ) confirming adipose tissue lipolysis during sleep. While RHI did not differ between CPAP/OSA, the extent of FFA elevation correlated with the decrease in RHI ( $r=0.51$ ,  $p<0.05$ ).

Mixed model analysis demonstrated that the nocturnal FFA dynamically changed with heart rate, but not with apnea hypopnea index (AHI),  $\beta=0.0043$  mmol per 1 BPM increase (CI: 0.001-0.0067;  $p=0.008$ ) after adjustment for AHI and BMI. This suggests that SNS activation may be the cause of lipolysis and hyperglycemia. In mice, we showed that exposure to intermittent hypoxia caused lipolysis, hyperglycemia, hyperlipidemia, and glucose intolerance, and many of these findings were abolished by propranolol [2]. Hence, the autonomic response to OSA, not a high AHI or low oxygen level *per se*, elicits excessive lipolysis, insulin resistance, and hyperglycemia during sleep. This physiology is consistent with the effects of OSA on blood pressure [18, 19] and the role of catecholamines in lipolysis, insulin resistance, and hyperglycemia in other forms of physical or emotional stress [20, 21].

**Our overarching hypothesis, diagrammed in fig 2, is that SNS activation in OSA causes lipolysis, hyperglycemia, insulin resistance, vascular dysfunction and that beta blockade will abolish these consequences.** This challenges the prevailing theory that intermittent hypoxia directly mediates metabolic pathology in OSA, through a mechanism comparable to ischemia-reperfusion injury [3]. If SNS activation mediates metabolic dysfunction in OSA, then beta blockade could become a cornerstone therapy for control of OSA consequences. Perhaps, the limited benefit of CPAP for secondary prevention of cardiovascular disease in those with established coronary artery disease is related to nearly ubiquitous use of beta blockers in this patient population [22, 23]. Dedicated study of beta blockade in OSA for metabolic health is therefore justified and of high clinical yield.

**Figure 2.** Hypothesis of this proposal – SNS activation during sleep causes glucose and lipid elevations and hyperglycemia, which in turn causes morning glucose intolerance vascular dysfunction.

The safety of this project is reinforced by the fact that beta blockers have been shown to attenuate OSA-induced hypertension [24, 25] without bradycardia or aggravating apnea-induced heart rate decelerations [26]. Beta blockade may similarly prevent stress-related changes in metabolism. We selected propranolol because it (1) is a non-selective beta antagonist that broadly inhibits norepinephrine-simulated lipolysis; (2) is lipophilic and crosses the blood-brain barrier, which may be desirable in mitigating OSA-related distress; (3) is well tolerated in non-hypertensive subjects [27]; (4) is effective in preventing hyperglycemia and/or lipolysis in other acute stresses including burn trauma [21], surgery [28], high altitude hypoxia [29] and animal models of autonomic stress [30] [31]; (5) and is mechanistically revealing, as it does not block alpha adrenergic receptors which are less likely to be involved in the stress hyperglycemic effect in humans [28].

#### 4. Study Procedures

- Study design, including the sequence and timing of study procedures

There are two primary interventions in this study: CPAP withdrawal and propranolol administration which are described below:

**CPAP withdrawal:** By manipulating CPAP, OSA can literally be switched “on” or “off” in the same individual, once they are accustomed to CPAP use[32]. This affords a straightforward means to study the isolated metabolic impact of OSA, using each patient as his or her own control. Based on CPAP withdrawal [33-36], or acute CPAP depressurization studies in our laboratory [32], OSA may not fully re-emerge until after a few days of cessation. Our preliminary data demonstrate that 3 nights of CPAP

withdrawal leads to a full recurrence of OSA and increases nocturnal FFA in a manner similar to that of treatment naïve patients [37]. CPAP withdrawal also induces the same sympathomimetic, neurocognitive, and vascular consequences of OSA as in treatment naïve subjects [33-36] indicating that findings of such studies are relevant to the untreated OSA population. Our 3 night CPAP withdrawal protocol has been approved by the Johns Hopkins IRB “Metabolic Impact of Intermittent CPAP” (8/5/2013). In this study, we use CPAP withdrawal to induce OSA, to provide a setting for testing a pharmacologic intervention designed to mitigate OSA consequences. To facilitate participant blinding of intervention, we will administer a nasal dilator strip (NDS) as a placebo during all CPAP withdrawal periods. NDS have been used in other studies as a CPAP placebo and have no impact on OSA severity [38].

[figure not shown]
**Propranolol administration:** Long acting propranolol LA (Inderal® LA) 80 mg or placebo will be given before sleep to suppress SNS responses to OSA. Propranolol LA has a 24-hour duration of effect which makes it suitable for this study, eliminating the need for repeated oral dosing.

**Study overview:** There are a total of 4 study visits. The first visit is a consent, screening, and randomization visit. After consent, a screening EKG will be performed to exclude rhythm or conduction abnormalities and a urine pregnancy test to exclude pregnancy in potentially pregnant females. (If the participant has had a clinical EKG or EKG report in the last year that does not indicate any conduction disorders listed in the exclusion criteria, the screening EKG may be deferred.) A point of care screening test for hemoglobin will also be performed to exclude pre-existing anemia. Patients with a hemoglobin < 10 g/dL are ineligible for this study. They will be provided with ClearPassage® NDS to use at home during CPAP withdrawal nights.

Thereafter, there are 3 overnight visits to the CRU in random order. This protocol compares nocturnal metabolism in treated OSA (CPAP), untreated OSA (NDS), and beta-blocked OSA (NDS) in the same subject. OSA nights are performed in the lab after using NDS instead of CPAP for 2 nights at home.

**Covid-19 screening:** We will screen participants before their arrival for their each sleep study with a Covid-19 test. A negative screen within 72 hours of the CPAP visit will be needed prior to admission for the CPAP study visit.

During each OSA visit, propranolol or placebo is taken in the evening, in random order. Frequent blood sampling is performed throughout the visit. In the morning, DEXA (only 1 DEXA needed for entire study) is performed. We are targeting 1 week between visits, but will allow flexibility in scheduling patients unable to schedule 3 consecutive visits exactly 1 week apart; in this scenario we will allow a duration of  $\geq$  4 days or  $\leq$  3 weeks between visits. Each visit we will also administer stable isotopes to measure detailed lipid metabolism.

#### Methods to minimize in-person contact:

In order to reduce the need for / length of research-only in-person visits, telemedicine visits will be substituted for in-person informed consent whenever logistically possible (However, we are aware that this will depend on the participants' familiarity, access to, and willingness to use telemedicine). Prior to initiating telemedicine for study visits the study team will explain to the participant, what a telemedicine

visit entails and confirm that the study participant is in agreement and able to proceed with this method. Telemedicine acknowledgement will be obtained in accordance with the Guidance for Use of Telemedicine in Research. In the event telemedicine is not deemed feasible, the study visit will proceed as an in-person visit. Telemedicine visits will be conducted using HIPAA compliant method approved by the Health System and within licensing restrictions.

[figure not shown]
Potential subjects will be provided with a copy of the Informed Consent form prior to the remote consent meeting either via email, fax, mail or previously provided during an in person visit. Potential subjects will then be contacted by phone by a consent designee to review the consent form in detail. Potential subjects will be given adequate time to consider the research study and ask questions prior to signing the consent form. The potential subject will then sign and date/time the informed consent document and it will be mailed, emailed or faxed to the consent designee, who will also sign/date/time. A copy of the fully signed CF will be returned to the volunteer

**Each sleep study night will consist of the following procedures:**

*Pre-sleep procedures.* Subjects will undergo a history and physical examination. They will report to the CRU at 4:00 PM and undergo anthropometric assessment including weight, height, neck, and waist circumference. At 5:30 PM, they will eat a standard dinner containing 30% fat, 50% carbohydrate, and 20% protein with kcal based upon the Mifflin-St Jeor formula. Two peripheral IVs (18 to 20 gauge) will be placed. All samples are obtained through the IV without disturbing the subject during sleep. Blood pressure will be checked at 6:30 PM, before administration of study drug. If systolic blood pressure is <90 or the heart rate is <50 then no drug will be administered. (In the event that this occurs, the study will still proceed so that CPAP and OSA nights can be compared and analyzed as a "no drug" group.) If blood pressure and heart rate are acceptable, propranolol LA 80 mg, or placebo (random order, crossover on study night 2 and 3) will be given. Participants and the investigators will be blinded to drug assignment.

*PSG setup.* On each study night from 10:30 PM until 6:30 AM, a PSG will be performed. The sleep study will include electroencephalography, electrooculography, oxygenation, respiratory effort, CPAP airflow, and transcutaneous CO2 monitoring. Respiratory effort will be measured by thoraco-abdominal movement assessed by mercury strain gauges. Surface electrodes will be placed at C3A2 and C3O1, a submental electrode, and left and right electro-oculogram will be used to stage sleep. Electrocardiograph (EKG) tracings will be recorded from three chest electrodes. Continuous measurement of oxygen saturation will be recorded using an ear oximeter (model No 472-1A, Hewlett Packard, Waltham, Mass). Transcutaneous CO2 will be monitored using a Radiometer TCM-4 device. Signals from the electroencephalograph, EKG, electromyogram, electrooculogram, respiratory strain gauge, ear oximeter and thermistors will be recorded on a computer with RemLogic software.

*Respiratory interventions.* During the CPAP night, patients will sleep using CPAP set to their prescribed home CPAP settings. Airflow will be recorded with a pneumotachograph in the CPAP circuit. CPAP will be titrated if necessary to prevent obstructive hypopneas and apneas. During NDS nights, ClearPassage® strips will be applied at bedtime. Flow will be measured using a nasal cannula and oral thermistor. Sleep and respiratory events will be scored according to AASM criteria. Apneas will be considered present when there is no air flow for >10 seconds. Obstructive apneas will be considered present when apneas are associated with positive strain gauge deflections indicating thoracic movement. Apneas will be considered central in origin when cessation of air flow is not accompanied by thoracic movement as measured by the strain gauge. Mixed apneas will be defined by episodes of no air movement resulting from central apnea followed by obstruction. Hypopneas will be scored for reductions in airflow of 30% lasting >10 seconds accompanied by either an arousal or fall in oxyhemoglobin saturation of 3% or greater. Blood pressure is measured at 7 PM, 10:30 PM, and upon awakening after the morning blood sample at 6:30 AM.

**Stable isotope ingestion and infusions.** Stable isotopes are being used in this project to quantify rates of adipose tissue lipolysis (infusions of [ $^{13}\text{C}_3$ ]glycerol and [ $^{13}\text{C}_{16}$ ]palmitate) and rates of fatty acid oxidation (FAO, ingestion of [ $^2\text{H}_{31}$ ]palmitate). Ingested  $^2\text{H}$  molecules on palmitate are incorporated into plasma  $^2\text{H}_2\text{O}$  during FAO and detected by mass spectrometry. This technique permits FAO measurement without needing to capture exhaled  $\text{CO}_2$ , measure  $\text{VCO}_2$ , or administer acetate to adjust for  $\text{CO}_2$  sequestration. By adopting this approach, FAO can be assessed without interrupting sleep, respiratory monitoring, or CPAP. **Catheters:** Before dinner, an IV will be inserted into a vein of each arm; one for blood sampling, and the other for infusion of labeled glycerol and palmitate. Patency of all catheters will be maintained by saline infusion. **Infusions of tracers:** On each visit, after obtaining a blood sample to determine background enrichment, a constant infusion of [ $^{13}\text{C}_3$ ]glycerol ( $0.1 \mu\text{mol}\cdot\text{kg}^{-1}\cdot\text{min}^{-1}$ ; Sigma-Aldrich, St. Louis, MO) will be administered. Glycerol and palmitate stable isotopes are obtained as a sterile powder from Sigma-Aldrich, and compounded and dispensed by the Johns Hopkins research pharmacy. The product is initially tested for sterility and pyrogenicity by Sigma-Aldrich. In the Johns Hopkins research pharmacy, the powders will be solubilized and aliquots tested for sterility and pyrogenicity. Infusions are given at a “tracer” dose detectable only by gas chromatography/mass spectroscopy (GC/MS). All tracers in this protocol are tested for microbiological contamination, and are exempt from FDA IND status (see correspondence with FDA # PIND 132066).

Blood samples will be collected at the intervals depicted (every 30-60 min, with additional samples towards end of each palmitate infusion period to verify isotopic steady-state) and analyzed for isotope enrichment by gas chromatography-mass spectrometry (GC/MS). Infusion of [ $^{13}\text{C}_3$ ]glycerol and quantification its enrichment in plasma of will be used to calculate lipolysis ( $R_a$  glycerol) throughout the night. Infusion of [ $^{13}\text{C}_{16}$ ]palmitate ( $0.04 \mu\text{mol}\cdot\text{kg}^{-1}\cdot\text{min}^{-1}$ ; Sigma-Aldrich, St. Louis, MO ) will be infused for 1-hour intervals at 9-10 PM (pre-sleep), 12-1 AM (early night), 5-6 AM (late night), and 8-9 AM (awake). Palmitate isotope will be bound to human albumin prior to infusion to facilitate steady-state infusion rates. Plasma enrichment of [ $^{13}\text{C}_{16}$ ]palmitate will be measured by GC/MS and used to calculate FFA turnover.  $R_a$  glycerol and  $R_a$  palmitate will be calculated from non-steady state Steele equations.  $R_a$  FFA will be derived from  $R_a$  palmitate based on the fractional contribution of palmitate to the total FFA concentration, as determined by GC.  $R_a$  FFA will be determined for each of the four infusion periods based on the average plasma [ $^{13}\text{C}_{16}$ ]palmitate enrichment during the last 3 samples of each infusion period.

**Ingestion of [ $^2\text{H}_{31}$ ]palmitate:** Conventional FAO assessment requires breath collection (e.g. enrichment of  $^{13}\text{CO}_2$  from infused [ $^{13}\text{C}$ ]palmitate), and calorimetry which would disrupt sleep, respiratory monitoring,

and CPAP airflow. Therefore, we use a validated technique to quantify differences in FAO between studies by providing an oral liquid dose of 15 mg/kg body mass of [H31]palmitate taken with dinner. The isotope is dissolved in a warm (60 °C) liquid shake (such as Ensure®). The isotope is non-radioactive and synthetic (Cambridge Isotope Laboratories DLM-215-MPT). FAO will be quantified thereafter by hourly assessment of deuterium incorporation into plasma H2O using anisotope ratio MS (IR/MS). Subjects will also ingest 0.4 g/kg body mass of H2O (10% enriched; CIL OLM-240-10-0, Andover MA) to calculate total body water (TBW) by isotope dilution. The FAO rate will be determined by excess plasma H times TBW, while percent recovery of deuterium will be determined by dividing by dose of H administered. All tracers in this protocol are tested for microbiological contamination, and are exempt from FDA IND status (see email correspondence with FDA # PIND 132066). The isotopes of H O and [H31]palmitate are stored in the PI's laboratory. Their required amount is prepared for each participant and brought to the CRU. The [H31]palmitate is dissolved in an Ensure shake and heated in the kitchen by nursing staff or dietitian in CRU.

*Blood sampling and morning urine sample collection.* The first blood sample is taken at 5:30 PM, just before dinner and serves as a pre-medication, pre-isotope baseline. Subsequent samples are drawn hourly while the subject is awake. At 10:30 PM, when the sleep study starts, blood is sampled more frequently, at 30 minute intervals in order to capture dynamic changes in metabolism during sleep. Additional samples will be drawn towards the end of each palmitate infusion period, to ensure a plateau of isotope enrichment. Each blood sample will be 4 cc in volume and placed into lavender top tubes (EDTA) for centrifugation to obtain plasma. Cells are removed from plasma by centrifugation for 10 minutes at 1500 x using a refrigerated centrifuge. Following centrifugation, plasma will be transferred to cryovials for storage. In patients that have signed the optional consent for isolation of genetic material, we will collect an additional 16 cc (4 tubes) at 6:30 AM upon awakening since this volume is required for isolation of peripheral mononuclear cells. The final sample is obtained at 9:00 AM. .

In total, the blood collected will be approximately 30 samples x 4 mL = 120 mL. For patients that consent to isolation of genetic material, the total will be 136 cc. This quantity is less than half the volume of blood given during a donation (350 mL). A morning urine sample will be collected for measurement of catecholamines. The final blood sample will be drawn at 9 AM, after which the IV will be removed, and the subject will be discharged from the CRU. Samples will be frozen at -80°C for research pertaining to metabolic effects of OSA, with the consent of participants.

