### Data Analysis and Anticipated Outcomes:

The primary outcomes are nocturnal glucose and FFA levels. The main independent variable is experimental condition: [CPAP], [OSA+placebo], or [OSA+propranolol]. Since glucose and FFA are measured multiple times per subject per night, we will perform mixed linear model analysis using condition as a fixed factor and subject ID as a random factor. We will also examine whether there are independent or interacting effects of time, or time x condition on trajectories of FFA and glucose. We hypothesize that OSA increases glucose and FFA levels during [OSA + placebo] nights, compared to [CPAP], or [OSA + placebo] nights. We further hypothesize that propranolol will suppress nocturnal FFA and glucose to levels similar to that of CPAP. Sleep physiology that is measured on a continuous basis will be condensed into 30 minute bins to create a parallel data structure with metabolic parameters. We will then examine whether sleep physiology (e.g. AHI, arousals, heart rate) is dynamically associated with glucose or FFA, and whether urine catecholamine levels are associated with increases in FFA or glucose. For variables measured once (RHI, morning lipid profile) or averaged together (e.g. nocturnal glucose level) we will perform one-way ANOVA for comparisons. We will also compare sleep physiology between the 3 nights, examining variables such as apnea hypopnea index, metrics of hypoxia, and sleep architecture/duration. A questionnaire will be administered each morning to assess subjective sleep quality from the night prior, and to screen for any symptoms related to study medication. These responses will be used to determine how symptomatic a subject's OSA is, whether subjective sleep quality correlates with extent of metabolic change, and whether any side effects of beta blockade were perceived.

Regarding tracer data, we predict that  $R_a$  FFA and  $R_a$  glycerol will exhibit a ~3:1 ratio reflecting typical patterns of lipolysis without significant intra-cellular recycling. Based on studies of normal sleep [39, 40], we predict that on CPAP, sleep reduces lipolysis and FAO compared to wakefulness. During CPAP withdrawal, sleep will increase lipolysis (or at least mitigate sleep-induced suppression) compared to wakefulness. We hypothesize that FAO will be reduced or unchanged by OSA. This pattern of increased lipolysis without increased FAO may lead to

ectopic lipid deposition and extracellular TG cycling (see figure).

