**7. Study Statistics**

- a. Primary outcome variable: Nocturnal FFA and glucose profile
- b. Secondary outcome variables: Morning EndoPAT, lipid panel. Sleep study parameters (e.g. total sleep time, latency, wake after sleep onset, sleep stages, AHI, oximetry, heart rate). Lipid flux data (rate of lipolysis and FFA turnover using stable isotope data; rate of fatty acid oxidation), DNA methylation profile.
- c. Statistical plan including sample size justification and interim data analysis.

**Comparisons between CPAP, [NDS + propranolol], and [NDS + Placebo]:** Primary outcome is comparison of metabolism and blood pressure for [NDS + propranolol] versus [NDS + placebo]. For metabolic parameters that are repeatedly measured during sleep (e.g. FFA, glucose) we will use mixed linear model analysis with experimental group as a fixed factor and subject ID as a random factor. Sleep physiology that is measured on a continuous basis (e.g. heart rate, AHI, SpO2) will be condensed into 30 minute bins to create a parallel data structure with metabolic parameters. We will then examine whether these sleep physiological metrics are dynamically associated with glucose/FFA level. For those parameters that are measured once per visit (e.g. RHI, lipid panel), we will compare using paired T-tests for within-subject comparisons between nights. A secondary outcome is whether CPAP and [NDS + propranolol] are similar, and this will be performed using a similar pairwise comparison. In addition, one way ANOVA will be used to ascertain whether there is a detectable difference across all three groups. Multiple regression will be used to examine associations between FFA, glucose, CPAP status, and drug adjusting for potential confounders such as diabetes, BMI, body fat (DEXA) and age. As an exploratory analysis, Pearson correlation matrices will be used to probe the interrelatedness of glucose, FFA, insulin, lipids, and sleep outcomes, followed by targeted multivariable regression. We plan an analysis of each subject's pulse rate and blood pressure after their PSG to determine whether beta blocker dosage or timing requires adjustment, which will expedite the ability to tailor the therapy if necessary.

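### The protocol randomises the order of all three overnight visits in one place and confines drug and placebo to nights 2 and 3 in another; if CPAP is fixed first, its CPAP contrasts are confounded with night order

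*Protocol*

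**What the plan says.** Two parts of Protocol section 4 describe the visit order.

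- **Study overview:** "Thereafter, there are 3 overnight visits to the CRU in random order". The text then names the three conditions as treated OSA on CPAP, untreated OSA with nasal strips, and beta-blocked OSA with nasal strips. It adds: "During each OSA visit, propranolol or placebo is taken in the evening, in random order".
- **Pre-sleep procedures:** if blood pressure and heart rate allow, propranolol LA or placebo is given in "random order, crossover on study night 2 and 3".

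The Protocol plans several comparisons that involve CPAP. Under Data Analysis and Anticipated Outcomes, condition has three levels, one of them CPAP, and the method is "mixed linear model analysis using condition as a fixed factor and subject ID as a random factor". The same section hypothesises that OSA raises FFA and glucose relative to CPAP, and that propranolol brings them back to about the CPAP level. Section 7 adds: "A secondary outcome is whether CPAP and [NDS + propranolol] are similar". It also says that "one way ANOVA will be used to ascertain whether there is a detectable difference across all three groups".

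None of these models contains a visit or night-order term. The time effect in Data Analysis and Anticipated Outcomes is time within the night.

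The SAP describes a two-condition crossover of propranolol against placebo and plans no CPAP comparison.

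**The concern.** The two statements describe different designs. In one, CPAP takes each of the three positions at random, so comparisons with CPAP are randomised. In the other, CPAP always holds the same position, and only the order of drug and placebo is randomised.

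In the second design, whatever is particular to the first laboratory night belongs to CPAP alone: the first experience of two IV lines, PSG leads and sleeping in the unit. The Protocol's own reasoning makes such an effect plausible. It attributes nocturnal rises in FFA and glucose to sympathetic activation, and it uses a sham device partly to control anxiety before sleep. It does not mention a first-night effect.

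At stake is whether the Protocol's statements about CPAP, namely that OSA is worse than CPAP and that propranolol restores CPAP-like levels, rest on randomised comparisons. As written, a reader cannot tell.

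**Working it through.** **1. Can both statements hold?** If three conditions are placed on three nights at random with equal chance, CPAP is on night 1 in one third of participants, and a drug or placebo night is on night 1 in the other two thirds. If drug and placebo are confined to nights 2 and 3, that share is zero. The statement that drug or placebo is taken in random order at OSA visits fits either schedule. If nights 2 and 3 meant visits 2 and 3 of the four study visits (visit 1 being consent), CPAP would always be last, and its position would still be fixed.

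**2. What can be estimated?** Take the Protocol's target of 30 subjects and a model with 30 subject terms, 2 condition terms and 2 night terms, 34 columns in all.

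| Design | Rank | CPAP - placebo | CPAP - propranolol | Propranolol - placebo |
|---|---|---|---|---|
| Six balanced sequences | 34 of 34 | estimable | estimable | estimable |
| CPAP always first | 33 of 34 | not estimable | not estimable | estimable |

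The lost rank arises because the CPAP indicator equals the night-1 indicator in every row. Each estimable contrast has variance 2/30 = 0.0667 in units of the residual variance, so propranolol minus placebo has the same precision in both designs.

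**3. Where does a night-1 shift go if there is no night term?** Let night 1 shift FFA by g.

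- Six balanced sequences: each condition is on night 1 in one third of subjects, so each condition mean moves by g/3. The bias in any contrast is g/3 - g/3 = 0.
- CPAP always first: CPAP moves by g and the other two conditions by 0. The bias in CPAP minus placebo and in CPAP minus propranolol is g. The bias in propranolol minus placebo is 0.

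**4. Scale.** The inputs are from Protocol section 7, Sample size: mean FFA 0.413 on CPAP and 0.447 on OSA with placebo (3 patients), and a standard deviation of 0.076 for the paired placebo-propranolol difference. I assume that this standard deviation also applies to CPAP differences. The shifts are assumptions too, since the documents give none.

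- Pilot OSA-CPAP difference: 0.447 - 0.413 = 0.034 mmol/L.
- Standard error with 30 subjects: 0.076/sqrt(30) = 0.0139 mmol/L.

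The table gives false-positive rates for CPAP versus placebo with no true effect (two-sided paired t-test at 0.05, 4,000 simulated trials, no night term).

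| Assumed g (mmol/L) | g / 0.0139 | CPAP first: bias | CPAP first: false positives | Six sequences: false positives |
|---|---|---|---|---|
| 0.015 | 1.08 | 0.015 | 18% | 4% |
| 0.03 | 2.16 | 0.030 | 55% | 4% |
| 0.06 | 4.32 | 0.060 | 99% | 2% |

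With CPAP first, propranolol versus placebo showed no bias and 4 to 5% false positives throughout.

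**The case against.** **The main comparison is not touched.** This stands in full. The Protocol says "Primary outcome is comparison of metabolism and blood pressure for [NDS + propranolol] versus [NDS + placebo", and the SAP's tests and models compare drug with placebo only. That contrast is randomised whether the order covers three nights or two. A reader might infer that the trial's principal result is compromised, but nothing in the documents supports that.

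**CPAP first is not established.** This also stands. A reader might conclude that CPAP was in fact always night 1. The evidence is one parenthesis, which the study overview contradicts. The night numbers may have been meant loosely, as labels for the two nasal-strip nights, and a figure not reproduced in the text may show the order. What the documents establish is a contradiction. The confounding is its consequence under one reading.

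**The size is assumed.** A reader might divide an assumed shift by 0.034 and report the result as the share of the CPAP effect at risk. The documents cannot support such a percentage: no first-night effect is given, and 0.034 is a difference of means from 3 patients with stated spreads of 0.107 and 0.084.

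**The direction is open.** If an unfamiliar night raised FFA, as the Protocol's stress hypothesis would suggest, CPAP values would rise. The OSA-CPAP difference would then shrink, which works against the Protocol's hypothesis. The comparison of CPAP with propranolol would still be distorted. The documents do not state the direction.

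**Some adjustment is possible.** It would be too strong to say that no analysis could separate CPAP from night order. If the night effect were a straight line, the crossover on nights 2 and 3 would estimate its slope, which could be carried back to night 1. That is a strong assumption, and adaptation confined to the first night would violate it. For an unrestricted night effect the separation is impossible.

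**Conclusion.** The contradiction within Protocol section 4 is real and is not resolved in the text available. Following the pre-sleep procedures literally aliases CPAP with night 1. An unrestricted night effect would then pass in full into the OSA-versus-CPAP hypothesis and the secondary CPAP versus [NDS + propranolol] comparison, and it would contaminate the three-group ANOVA. The algebra rests only on CPAP being fixed first. The false-positive rates of about 18% to 99% rest further on assumed shifts of 0.015 to 0.06 mmol/L, a standard deviation borrowed from 3 pilot patients, and 30 analysed subjects. They show sensitivity and do not predict what happened.

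This is a moderate point. It decides whether the CPAP findings can be called randomised evidence, and it leaves propranolol versus placebo and every SAP analysis as they are.

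**What to change.** Check the allocation list to see which sequences were used, reconcile the study overview with the pre-sleep procedures, and state the sequences explicitly. The documents do not show which sentence is wrong, so neither should be deleted before that check.

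- **If all three nights were randomised:** correct the pre-sleep procedures and add visit number as a fixed effect to the three-condition models. The cost is a sentence and two model degrees of freedom.
- **If CPAP was always first:** correct the study overview and report every CPAP contrast as non-randomised and confounded with night order. A linear-trend adjustment could be shown as a sensitivity analysis, with its assumption stated.

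In the second case the CPAP conclusions become weaker. Data already collected cannot be repaired: the Protocol reports 3 completed patients, and the SAP refers to participants already enrolled.
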